9.6. Data Management

Statistical analyses will be performed using Statistical Analysis System (SAS) Version 9.4 (SAS Institute, Cary, NC) and STATA Version 15 (StataCorp, LP, College Station, TX).

9.7. Data Analysis

Patients initiating tofacitinib during or after February 2016 with a six-month follow-up visit (+/- 3 months) will be considered for analysis. Patient and disease characteristics at initiation for the two cohorts of 11 mg QD and 5 mg BID will be considered. Propensity score matching and adjustment for covariates will be used to identify a balanced, matched subset of patients to use in final analyses.

The primary outcome will be minimum clinically important difference (MCID) improvement as defined by difference in CDAI from initiation to 6 month visit (dichotomous variable). Secondary outcomes at the 6 month visit (follow-up): change in CDAI from initiation to follow-up, achievement of remission ($CDAI \leq 2.8$) and achievement of low disease activity (LDA) ($CDAI \leq 10$), achievement of improvement from baseline to follow-up in HAQ of 0.22 and change from baseline to 6 month follow-up HAQ, modified DAS, DAS ESR, DAS CRP, patient pain, patient fatigue, EQ5D index, modified ACR20/50/70. Sensitivity analysis, will be performed if needed.

Detailed methodology for the original analysis as well as all subsequent analyses is documented in respective SAPs, which are dated, filed and maintained by Pfizer. The SAP may modify the plans outlined in the protocol; any major modifications of primary endpoint definitions or their analyses would be reflected in a protocol amendment.

9.8. Quality Control

The Corrona registry has standard operating procedures in place to monitor, perform edit and logic checks, and make corrections to the data, as necessary. Specifically, the data for each site is reviewed by the Quality Department or other delegated Corrona representative for completeness and internal consistency at regular intervals. The Quality Department generates a list of queries for each site, sends to the clinical site coordinator, and requests verification or correction for each query within 14 days. The Quality Department or other designated Corrona representative enters corrected data onto the Corrona database. An audit trail of all corrections to the data, and the personnel making and date of corrections, is stored with the data in the Corrona database.

9.9. Limitations of the Research Methods

This study has a number of limitations. Patient characteristics and access to medications can vary substantially between countries, due to payer and regulatory differences, thus these results may be less applicable outside of the US. Propensity score (PS) methods are intended to adjust for non-random treatment assignment, however, the possibility of bias and endpoint misclassification remains for observational studies. Furthermore, while we accounted for the most clinically significant variables, unmeasured residual confounding is a possibility.

9.10. Other Aspects

Not applicable.

10. PROTECTION OF HUMAN SUBJECTS

10.1. Patient Information

This study involves data that exist in anonymized structured format and contain no patient personal information.

10.2. Patient Consent

As this study involves anonymized structured data, which according to applicable legal requirements do not contain data subject to privacy laws, obtaining informed consent from patients by Pfizer is not required.

10.3. Institutional Review Board (IRB)/Independent Ethics Committee (IEC)

IRB/IEC approvals/waivers not required.

10.4. Ethical Conduct of the Study

The study will be conducted in accordance with legal and regulatory requirements, as well as with scientific purpose, value and rigor and follow generally accepted research practices described in Guidelines for Good Pharmacoepidemiology Practices (GPP) issued by the International Society for Pharmacoepidemiology (ISPE), Good Epidemiological Practices (GEP) guidelines issued by the International Epidemiological Association (IEA).

11. MANAGEMENT AND REPORTING OF ADVERSE EVENTS/ADVERSE REACTIONS

This study involves data that exist as structured data by the time of study start.

In these data sources, individual patient data are not retrieved or validated, and it is not possible to link (ie, identify a potential association between) a particular product and medical event for any individual. Thus, the minimum criteria for reporting an adverse event (AE) (ie, identifiable patient, identifiable reporter, a suspect product, and event) cannot be met.

12. PLANS FOR DISSEMINATING AND COMMUNICATING STUDY RESULTS

In the event of any prohibition or restriction imposed (eg, clinical hold) by an applicable competent authority in any area of the world, or if Corrona becomes aware of any new information which might influence the evaluation of the benefits and risks of a Pfizer product, Pfizer should be informed immediately.

The protocol will be disclosed at clinicaltrials.gov website along with the final study results. In addition, the study results will be submitted to national and international medical conferences and a final publication will be developed and submitted to an indexed, peer-reviewed medical journal in the area of rheumatology. Results from the interim/full analysis may also be reported to European Medicines Agency (EMA) to support MR submission.

15. LIST OF FIGURES

Not applicable.

ANNEX 1. LIST OF STAND ALONE DOCUMENTS

None.

ANNEX 2. ENCEPP CHECKLIST FOR STUDY PROTOCOLS

Not applicable.

ANNEX 3. ADDITIONAL INFORMATION

Not applicable.

## Statistical Analysis Plan

**Title:** Efficacy analysis of Tofacitinib 11 mg QD compared with Tofacitinib 5 mg BID initiators

### Background:

Tofacitinib (tofa) 11 mg QD was approved in February 2016. It is hypothesized that this formulation will behave similarly to the Tofacitinib 5 mg BID dosage in terms of efficacy.

### Overall Aim:

Compare efficacy of Tofacitinib 11 mg QD initiators to Tofacitinib 5 mg BID initiators

### Overall Aim Population:

Initiators of tofa 11 mg QD

Initiators of tofa 5 mg BID

### Primary Outcome for Overall Aim:

Minimally clinically important difference (MCID) improvement as defined by difference in CDAI from initiation to 6 month visit (dichotomous variable). MCID is dependent on baseline disease activity (at initiation); MCID $\geq$ 2 if CDAI at initiation of Low CDAI  $\leq$  10, MCID $\geq$  6 if CDAI at initiation Moderate of  $10 < \text{CDAI} \leq 22$  and MCID $\geq$ 11 if CDAI at initiation High of  $> 22$ .

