9.2.1. Inclusion Criteria

Patients must meet all of the following inclusion criteria to be eligible for inclusion in the study:

1. All US Corrona RA Registry patients who initiated tofacitinib 5 mg BID or tofacitinib 11 mg QD after it became available in February 2016.

2. Patients must have a follow-up visit at 6 months (+/- 3 months) after tofacitinib initiation. These 6 month visits are part of routine practice and is not associated with this protocol.
3. Patients must have a valid clinical disease activity index (CDAI) at initiation and at 6-month follow-up visit.

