9.2.2. Exclusion Criteria

There are no exclusion criteria for this study.

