9.3. Variables

The US Corrona RA Registry is an efficient data collection system for evaluating a range of efficacy outcomes associated with therapies used to treat RA. The endpoints chosen for this study will be extracted from patient and physician questionnaires. Demographic data collected includes age, gender, race and ethnicity. In addition, baseline disease characteristics like disease duration and severity etc. will be captured for both the IR and MR cohorts under study to evaluate disease characteristics.

Primary outcome: Minimally clinically important difference (MCID) improvement as defined by difference in Clinical Disease activity index (CDAI) from initiation to 6 month visit. MCID is dependent on baseline disease activity (at initiation); $MCID \geq 2$ if CDAI at initiation of Low $CDAI \leq 10$, $MCID \geq 6$ if CDAI at initiation Moderate of $10 < CDAI \leq 22$ and $MCID \geq 11$ if CDAI at initiation high of > 22 .

Secondary Outcomes:

- Change in CDAI from baseline to 6 month follow-up (as a continuous variable).
- Achievement of Remission ($CDAI \leq 2.8$) at 6 month follow-up (among all).
- Achievement of Remission ($CDAI \leq 2.8$) at 6 month follow-up (among those that were not in remission at initiation).
- Achievement of Low Disease Activity (LDA) ($CDAI \leq 10$) at 6 month follow-up (among all).
- Achievement of Low Disease Activity (LDA) ($CDAI \leq 10$) at 6 month follow-up (among those that were not in remission or LDA at initiation).
- Achievement of improvement from baseline to 6 month follow-up in modified Health Assessment Questionnaire (mHAQ) of at least 0.25 (as a dichotomous variable).
- Achievement of improvement from baseline to 6 month follow-up in Health assessment questionnaire (HAQ) of at least 0.22.

- Change from baseline to 6 month follow-up HAQ (HAQ as a dichotomous variable).
- Change from baseline to 6 month follow-up modified HAQ (mHAQ as a continuous variable).
- Change from baseline to 6 month follow-up HAQ (HAQ as a continuous variable).
- Change from baseline to 6 month follow-up modified Disease activity Score (mDAS as a continuous variable).
- Change from baseline to 6 month follow-up Disease activity score- erythrocyte sedimentation rate (DAS ESR) (as a continuous variable).
- Change from baseline to 6 month follow-up DAS- C- reactive protein (DAS CRP) (as a continuous variable).
- Change from baseline to 6 month follow-up patient pain (as a continuous variable).

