**Table 1 continued**

At time of Tofacitinib initiation	11 mg QD N=	5 mg BID N=	Standardized difference
Prior TNF Use			
0			
1			
2+			
Prior non-TNF Use			
0			
1			
2+			
Prior Biologic Use			
0			
1			
2			
3+			
Current concomitant therapy			
Monotherapy			
Combo w/MTX alone			
Combo w/other cDMARD (not MTX)			
Combo w/MTX + other cDMARD			
Current medication at the time of initiation			
Prednisone use: n (%)			
Prednisone dose among users			
≤10 mg			
>10 mg			
Disease Activity: Mean ± SD			
Tender Joint Count (28)			
Swollen Joint Count (28)			
Physician Global Assessment (0-100)			
Patient Global Assessment (0-100)			
CDAI			
Disease activity category			
Remission (CDAI ≤ 2.8)			
Low (2.8 < CDAI ≤ 10)			
Moderate (10 < CDAI ≤ 22)			
Severe (CDAI > 22)			
Patient Pain (0-100)			
Patient reported fatigue (0-100)*			
EQ-5D (0-1)			
mDAS: Mean ± SD			
DAS ESR: Mean ± SD			
DAS CRP: Mean ± SD			

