**Table 1 continued**

At time of Tofacitinib initiation	11 mg QD N=	5 mg BID N=	Standardized difference
Line of therapy			
1 st			
2 nd			
3 rd			
4 th			

SD = Standard Deviation

IQR = Interquartile Range: 25th percentile, 75th percentile

Standardized differences rather than p-values can be more informative regarding the actual size of the difference between the two groups; hence, it is suggested that they be used rather than p-values to inform which variables are to be included in the propensity score model.

\*The scale ranges from 0-100 with 0 being fatigue is no problem to 100 fatigue is a major problem.

**Table 1a. Patient Demographic and Clinical Characteristics for Tofacitinib Initiators by Dose (5 mg BID and 11 mg QD) after Propensity Score Matching.**

Repeat Table 1 in the Propensity Score Matched cohort. *Table only generated for the final analysis.*

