**Table 2b: Additional information on MCID improvement**

*Table generated "after propensity score matching" only for the final analysis.*

	11 mg QD Initiators N=	5 mg BID Initiators N=
Measure	Response Rate	Response Rate
Percent achieving MCID $\geq 2$ if CDAI at initiation is low (CDAI $\leq 10$ )		
Percent achieving MCID $\geq 6$ if CDAI at initiation is moderate ( $10 < \text{CDAI} \leq 22$ )		
Percent achieving MCID $\geq 11$ if CDAI at initiation is high ( $> 22$ )		

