**Table 4 continued**

At time of Tofacitinib 5 mg initiation	Patients that switched from Tofacitinib 5 mg BID to Tofacitinib 11 mg QD N=
Prior non-TNF Use	
0	
1	
2+	
Prior Biologic Use	
0	
1	
2	
3+	
Current concomitant therapy	
Monotherapy	
Combo w/MTX alone	
Combo w/other cDMARD (not MTX)	
Combo w/MTX + other cDMARD	
Current medication at the time of initiation	
Prednisone use: n (%)	
Prednisone dose among users	
≤10 mg	
>10 mg	
Disease Activity: Mean ± SD	
Tender Joint Count (28)	
Swollen Joint Count (28)	
Physician Global Assessment (0-100)	
Patient Global Assessment (0-100)	
CDAI (0-76): Mean ± SD	
Disease Activity Category: N (%)	
Remission (CDAI ≤ 2.8)	
Low (2.8 < CDAI ≤ 10)	
Moderate (10 < CDAI ≤ 22)	
Severe (22 < CDAI)	
Patient Pain (0-100)	
Patient reported fatigue (0-100)	
EQ-5D (0-1)	
mDAS: Mean ± SD	
DAS ESR: Mean ± SD	
DAS CRP: Mean ± SD	

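### Should the primary MCID analysis separate patients whose baseline CDAI is below 2 and who therefore cannot respond?

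*SAP*

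**What the plan says.** Protocol section 9.3 states that "MCID is dependent on baseline disease activity (at initiation" and gives three bands. The SAP repeats them under Primary Outcome for Overall Aim. The lowest band reads "MCID $\geq$ 2 if CDAI at initiation of Low CDAI" and covers every baseline of 10 or below. The other bands need a fall of at least 6 (above 10, up to 22) and at least 11 (above 22).

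The scale range appears in SAP Table 4 as "CDAI (0-76): Mean ± SD". Protocol 9.2.1 asks only for a valid measurement: "Patients must have a valid clinical disease activity index (CDAI) at initiation and at 6-month follow-up visit". Protocol 9.2.2 adds: "There are no exclusion criteria for this study".

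The SAP handles baseline differently elsewhere:

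- HAQ and mHAQ response is calculated only in patients whose baseline is at or above 0.22 and 0.25 (footnotes to Tables 3, 3_adj and 5).
- Remission and LDA are each shown for all patients and for those not already there.
- MCID is shown overall (Tables 2 and 2_adj) and by band (Table 2b). The first row of Table 2b applies "if CDAI at initiation is low", meaning 10 or below.
- Table 1 has a baseline row "Remission (CDAI ≤ 2.8" by group, and for Table 1a the instruction is: "Repeat Table 1 in the Propensity Score Matched cohort".

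**The concern.** A fall in CDAI cannot exceed the starting value. A patient who starts at 1.5 and stays there for six months is scored as a primary failure, although remission has been maintained. The SAP excludes such patients from HAQ and mHAQ response, but no readable text does so for the primary outcome.

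If a share f of each group starts below 2, the risk difference among patients able to respond is multiplied by (1 − f). The study's hypothesis is that the two regimens are similar, so shrinkage works in favour of the expected conclusion. Matching or adjusting for baseline CDAI limits imbalance in f between groups but does not undo shrinkage common to both. At stake would be a real difference that is understated, with nothing beside the primary result to show by how much.

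**Working it through.** **Inputs.** From the sample size text (Protocol 9.5; SAP Appendix): 50% meeting MCID, a 15-point difference, 90% power, alpha 5% (two-sided assumed), 237 analysable per group. From the SAP's proposed analyses on the August 2019 registry version: 401 QD and 172 BID patients with an eligible visit, before the valid-CDAI requirement. The share f is not in the documents; I take 2%, 5% and 10%.

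**The plan's own figure.** For 50% against 65%, the pooled two-proportion formula with continuity correction gives 240 per group, close to the stated 237 (227 without the correction). Power at 237, without the correction, is 91.3%.

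**Shrinkage.** With rates of 50% and 65% among patients able to respond, the all-patient rates are 50(1 − f) and 65(1 − f), so the difference is 15(1 − f).

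| f | BID | QD | Difference | Shrinkage | Power at 237, all patients | Power at 237(1 − f), restricted |
|---|---|---|---|---|---|---|
| 2% | 49.0% | 63.7% | 14.7 | 0.3 | 90.0% | 90.7% |
| 5% | 47.5% | 61.75% | 14.25 | 0.75 | 87.9% | 89.9% |
| 10% | 45.0% | 58.5% | 13.5 | 1.5 | 83.9% | 88.2% |

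Shrinkage is f times the true difference, so it vanishes as the groups become alike. For a true 5-point difference at f = 10% it is 0.10 × 5 = 0.5 points.

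The fall in power applies only if 50% and 15 points describe patients able to respond. The sample size text makes no such restriction. Read plainly, it describes all patients, and planned power is unaffected.

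**Sampling error for comparison.**

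- 401 and 172: SE = √(0.65 × 0.35/401 + 0.25/172) = 4.50 points, half-width 1.96 × 4.50 = 8.8 points.
- Matched 1:1 (ratio not stated), at most 172 pairs: SE = √((0.2275 + 0.25)/172) = 5.27 points, half-width 10.3 points, ignoring any correlation within pairs.

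**Patients involved.** f × 401 = 8, 20 and 40 QD; f × 172 = 3, 9 and 17 BID.

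**Imbalance in f.** With a common 50% rate among patients able to respond, a 3-point gap in f produces a false difference of 0.5 × 3 = 1.5 points. A 3-point gap in the baseline remission row has a standardized difference |p − q|/√((p(1 − p) + q(1 − q))/2) of 0.16 (2% against 5%), 0.12 (5% against 8%) or 0.09 (10% against 13%). The SAP's threshold for considering a covariate is 0.1. Baseline CDAI is also listed for the propensity score and for the adjusted models.

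**What the planned tables already show.** The moderate and high rows of Table 2b contain no patient below 2. Combined with the category counts in Tables 1 and 1a, they give the MCID rate among patients with baseline CDAI above 10, by group. Objective 1 of the SAP addendum produces Table 2b for the full population as well. The baseline remission row is an upper bound on f, since it also holds patients from 2 to 2.8 who can respond.

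**The case for a change.** The best case for a change is consistency and low cost. HAQ and mHAQ are restricted for just this reason, and the primary outcome arguably deserves the same care. The low row of Table 2b could be split at 2, and MCID among patients starting at 2 or above could be shown as a sensitivity analysis on data already held. If f turned out large, readers would want to see it. Under the less natural reading of the sample size text, the restricted analysis also has slightly more power at each f above.

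Part of this stands. The floor is real, the HAQ and mHAQ comparison is apt, and neither the low row nor the overall rate isolates these patients.

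The rest is weaker. Remission and LDA are not true parallels: a patient already at target can still count as a success at six months, so those restrictions address the opposite problem. Nor does the SAP apply a general floor rule. The modified ACR outcomes need a percentage improvement in tender and swollen joint counts, which a zero count cannot show, and no baseline restriction is readable there.

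The gain is also thin. The new row below 2 would be 0% by definition and, at f of 2% to 5%, would hold some 3 to 9 BID patients. In the matched analysis, restriction would break pairs unless matching were redone and balance rechecked, and all of it would be added after earlier looks at the data.

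**Conclusion.** No change to the plan is needed. A patient who starts below 2 has not had an MCID improvement under the stated rule, so the scoring is right. The all-patient difference is what the analysis sets out to estimate. Remission and LDA among all patients credit maintained remission, Table 2b gives MCID free of the floor above a CDAI of 10, and Tables 1 and 1a bound the share affected.

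At an assumed f of 2% to 10%, a 15-point difference shrinks by 0.3 to 1.5 points, against a half-width of 8.8 to 10.3 points. The conclusion rests on f being modest. The documents give no count, though Protocol section 7 describes approval for moderate to severe disease, which suggests few such starters (registry practice may differ). At f = 20% the difference would be 12 points, and Table 1 would show a baseline remission row of at least that size.

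The absence of a restricted MCID analysis holds for readable text only. The Supplemental Analyses section and parts of the later addenda are redacted, and no non-inferiority table is readable.

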### Secondary Outcomes for Overall Aim:

- Change from baseline to 6 month follow-up CDAI (as a continuous variable)
- Achievement of Remission (CDAI $\leq$ 2.8) at 6 month follow-up (among all)
- Achievement of Remission (CDAI $\leq$ 2.8) at 6 month follow-up (among those that were not in remission at initiation)
- Achievement of Low Disease Activity (LDA) (CDAI $\leq$ 10) at 6 month follow-up (among all)
- Achievement of Low Disease Activity (LDA) (CDAI $\leq$ 10) at 6 month follow-up (among those that were not in remission or LDA at initiation)
- Achievement of improvement from baseline to 6 month follow-up in modified HAQ (mHAQ) of 0.25 (as a dichotomous variable)
- Change from baseline to 6 month follow-up modified HAQ (mHAQ as a continuous variable)
- Achievement of improvement from baseline to 6 month follow-up in HAQ of 0.22 (as a dichotomous variable)
- Change from baseline to 6 month follow-up HAQ (HAQ as a continuous variable)
- Change from baseline to 6 month follow-up modified DAS (mDAS as a continuous variable)
- Change from baseline to 6 month follow-up DAS ESR (as a continuous variable)
- Change from baseline to 6 month follow-up DAS CRP (as a continuous variable)
- Change from baseline to 6 month follow-up patient pain (as a continuous variable)
- Change from baseline to 6 month follow-up patient fatigue (as a continuous variable)
- Change from baseline to 6 month follow-up EQ-5D index (as a continuous variable)

- Modified ACR20, ACR50, ACR70

Please see Appendix for more details on the secondary outcomes.

Patients that switched to an agent other than tofa during the 6 months of follow-up will be considered for the continuous outcomes at the time of switch (rather than at 6 months).

In **Tables 2 and 3**, for the dichotomous primary and secondary outcomes, patients that discontinued or switched to an agent other than tofa will be considered as non-responders (e.g. did not achieve remission for patients that discontinued or switched prior to their 6 month visit).

## Analysis for Overall Aim:

Consider the demographic, patient and disease characteristics of the 11 mg QD initiators to the 5 mg BID initiators. Ideally, the two groups of patients would be from a similar timeframe, have similar disease activity, be of the same line of therapy and generally be similar aside from the fact that they have initiated tofa 11mg QD vs. tofa 5 mg BID. The goal is to create similar cohorts of patients with equal likelihood of response. The main objective behind this study design is to ensure that the two groups are similar prior to doing any comparisons of outcomes. Then, if differences in outcome are seen, we can be confident that they truly represent differences between the two groups and are not due to inherent dissimilarities between the two cohorts at baseline.

Patient and disease characteristics at initiation for the two groups will be reported in **Table 1** with standardized differences calculated. Standardized differences provide a measure of clinically important differences even if there is no statistically significant difference between the two groups. A standardized difference that is less than 0.1 is commonly taken to indicate a negligible difference between treatment groups. The most thorough approach to use if there is imbalance based on standardized differences is propensity score matching to account for these imbalances. If there are only a few differences, then accounting for these imbalances in the adjusted outcome analysis may be possible; however, propensity score (PS) matched would be a more robust approach and will be described here. For the initial look at the data, as number of patients is projected to be small, we would not recommend considering propensity score matching at that time. Rather, we would recommend adjusting for a small number of critical variables if needed. We expect to use PS matching in the final analysis and therefore it is described below.

CCI

Based on factors in **Table 1** that differ between the two groups (e.g. standardized difference > 0.1) and clinical input on a priori factors to include, a propensity score will be estimated for propensity of being in the 11 mg QD group. A small number of factors will be considered in the propensity score model; these may include age, gender, disease activity, line of therapy, etc. The primary purpose of the propensity score approach is to determine the patients with “common support” – those patients falling in an overlapping distribution of the propensity score. Patients falling outside the common support would have no comparable patients in the other group and would not be able to be used for comparative analyses.

Here we describe the propensity score matching approach.

***Propensity Score Matching Approach:*** To balance differences in baseline patient and disease characteristics among the 5 mg BID and 11 mg QD groups, we will use matched propensity scores.

***Logistic regression model approach to obtain propensity scores:*** We will use the logistic regression approach (outcome is 11 mg QD therapy) including variables such as the following covariates: age (continuous), gender (male is reference group), baseline CDAI (continuous), line of therapy (categorical), duration of disease (categorical), as appropriate. As mentioned above, we plan to examine all the Table 1 variables, but expect that only a select group will be considered in the propensity score model. The resulting logit model will be of the form:

$$\ln\left(\frac{p}{1-p}\right) = m_{11mgQD}$$

$$= \beta_0 + \beta_1 * age + \beta_2 * gender + \beta_3 * CDAI + \beta_4 * line\ of\ therapy + \dots$$

where  $p$  is the probability of 11mg QD Tofacitinib therapy.

A patient's resulting propensity score from the model is the patients predicted 11 mg QD Tofacitinib ( $p_{11mgQD}$ ), given by

$$p_{11mgQD} = \frac{e^{m_{11mgQD}}}{1 + e^{m_{11mgQD}}}$$

After the propensity score model is fit, **Table 1** will again be constructed with this propensity score matched sample and presented in **Table 1a** to ensure that there are no longer any statistically significant differences between the two groups (11 mg QD and 5 mg BID therapy). For the propensity score matching, it is proposed that a caliper of 0.01 will be used, but the caliper may be increased if the resulting sample size available from the propensity score matching is prohibitive.

In addition to considering the standardized differences between the individual characteristics of the two groups, we will also perform additional diagnostics plot to assess whether the overall distributions of the two groups are well-matched and under common support. These would include considering kernel-density plots and box plots to compare the two distributions. If they were not found to be sufficiently overlapping, we would consider revisiting the propensity score model to include additional covariates that might not have been originally included.

Once the propensity score matched sample is identified, the primary outcome of MCID of CDAI will be considered in **Table 2**. Table 2a will present the distribution of the switching status of patients. Secondary outcomes will be considered in **Table 3**.

